## 7.7. Unscheduled Visit (if needed)

An unscheduled study visit may be initiated by the subject/subject's LAR or investigator, if a subject is not improving on therapy, has a grade 2 and above AE/SAE/AESI, or for any other reason. In addition, the reason for the visit will be documented, including who initiated the visit, what complaints the subject/subject's LAR has, and/or what concerns the primary medical team or site investigator have. Clinical outcome and any safety assessments will be documented.

All assessments that should be completed at a scheduled visit will be completed including:

• Review of concomitant medications

- Assessment of study drug compliance if visit occurs before EOT visit
- Review of memory aid and assessment of solicited adverse events if visit occurs before EOT visit
- Assessment of cUTI signs and symptoms and investigator's assessment of improvement
- Limited physical exam (abdominal, flank, and suprapubic palpation, and examination of any other body site as indicated by subject symptomatology) with vital signs (blood pressure, heart rate, respiration rate, temperature)
- Collection of blood sample for blood culture if subject is febrile and/or at investigator's discretion
- Collection of urine specimen for culture as needed in the setting of clinical failure
- Collection of AEs grade 2 and above and AESI of any grade if visit occurs before EOT, or SAEs if visit occurs before TOC

## 7.8. Visit 02A: Visit for future use samples and data (if applicable)

Subjects who only received fosfomycin as part of Strategy 1 without any adjustment will be asked to have one additional optional visit and be willing to come back 24 hours later for EOT visit. The subject will be asked to bring the day's dose in and take it after the pre-dose sample is drawn. The visit will be done at Day 5-7 with the following procedures being performed

- Review of concomitant medications
- Assessment of study drug compliance
- Collection of AE grade 2 and above and AESI of any grade
- Measurement of weight
- Insertion of a peripheral intravenous catheter that will be removed by the end of the visit or performance of serial venipunctures per the participant's preference.
- Venous blood sample collection at collection at 0 (pre-dose) 0.5, 1, 2, 4 and 24 hours after the dose. The 24 hour collection will be done as part of EOT visit. Three mL of blood will be collected at each of these timepoints.
- Total voided urine collection between 0-4 hours and 4-24 hours post dose. The subject is asked to empty his/her bladder before taking the fosfomycin dose. The collection of the 4-24 hours urine will be done as part of EOT visit.

## 8. STUDY PROCEDURES/EVALUATIONS

#### 8.1. Clinical Evaluations

A focused medical history will be obtained by review of the subject's medical records or by interview of the subject or LAR. Medical history will be obtained regarding significant medical disorders of the head, eyes, ears, nose, throat, mouth, cardiovascular system, lungs, GI tract, liver, pancreas, kidney, urologic system, nervous system, blood, lymph nodes, endocrine system, musculoskeletal system, skin, and genital/reproductive tract. A history of any allergies, cancer, immunodeficiency, psychiatric illness, substance abuse, and autoimmune disease will be solicited.

Medications history (concomitant medications) will include a review of all current medications and medications taken within 30 days before signing the ICF through the TOC visit. Prescription and over-the-counter drugs will be included as well as herbals, vitamins, and supplements. Use of a new medication should prompt evaluation for the presence of a new AE or diagnosis of a chronic medical disease or condition.

The limited physical exam will include abdominal, flank, and suprapubic palpation, and examination of any other body site as indicated by subject symptomatology.

Vital signs will include (depending on the visit) subject's height and weight, blood pressure, heart rate, respiration rate, and temperature.

Assessment of cUTI signs and symptoms will be performed. Signs and symptoms to be assessed include fever, hypothermia, chills, flank pain, flank tenderness, suprapubic tenderness, vomiting, pain on urination, urinary frequency, urinary urgency, foul smelling urine, and cloudy urine.

A review of memory aids will be performed by assessing solicited events from randomization until EOT visit (and up to 2 days later if subject's last study drug dose is fosfomycin).

# 8.2. Laboratory Evaluations

## 8.2.1. Clinical Laboratory Evaluations

A urine or serum pregnancy test will be performed by the local laboratory within 48 hours of randomization to study drug in all women of childbearing potential. Results must be negative and known before randomization and administration of study drug.

Clinical screening laboratory parameters to be evaluated include:

• Serum chemistries (3 mL), including creatinine, blood urea nitrogen (BUN), glucose, sodium, potassium, chloride, bicarbonate, calcium will be performed at the local laboratory and, if obtained as standard of care, within 48 hours of randomization.

- Hematology (4 mL), including complete blood count (with RBC count, hemoglobin, and hematocrit, total WBC count with differential counts, platelet count), will be performed at the local laboratory and, if obtained as standard of care, within 48 hours of randomization.
- Urinalysis, including dipstick analysis and microscopic evaluation to assess WBCs, nitrites, leukocyte esterase and squamous epithelial cells, will be performed at the local laboratory and, if obtained as standard of care, within 48 hours of randomization.
- Liver studies (3 mL) including SGOT, SGPT, alkaline phosphatase, total bilirubin. LDH, albumin, total protein, PT and PTT are not required for the trial, but will be recorded if they are obtained by the primary medical team as standard of care.
- Screening blood cultures (32-40 mL) may be performed at the local laboratory. If blood cultures are positive the patient will be considered a treatment failure and referred to the primary provider of treatment.
- Urine cultures will be performed at the local laboratory at screening, EOT, TOC and early termination visit. If a subject fails treatment at any point during the trial, an adequate and appropriate urine specimen should be obtained for culture. Urine cultures will be performed at the local laboratory and positive cultures will be sent to central laboratory. At the Emory VTEU site, back-up bacterial isolate samples not needed by the central laboratory will be tested for heteroresistance in local research lab.

## 8.2.2. Special Assays or Procedures

N/A

#### 8.2.3. Specimen Preparation, Handling, and Shipping

#### 8.2.3.1. Instructions for Specimen Preparation, Handling, and Storage

Specific instructions are included in the Manual of Procedures.

#### **Bacterial Isolates**

Bacterial isolates that grew from urine culture collected within 72 hours prior to randomization (prior to any antimicrobial therapy) will be stored locally.

#### **Future Use Samples and Data**

Pre and post-dose blood will be collected in a K2EDTA tube. In addition, total voided urine will be collected over 4 hours during the PK visit then over 20 hours to be collected at home until the second PK visit.

Plasma samples will be processed by being centrifuged for plasma separation, aliquoted and stored as specified in MOP Appendix C.

The volume and pH of the urine will be measured for each collection (0-4 hours and 4-24 hours). Urine will be processed and aliquoted from each collection and stored as specified in MOP Appendix C.

## 8.2.3.2. Specimen Shipment

Specific instructions are included in the Manual of Procedures.

Bacterial isolates and future-use specimens (urine and blood) will be shipped under controlled conditions in compliance with the UN 3373 guidelines. Bacterial isolates will be batch shipped at room temperature on agar tubes to the Central Laboratory. At the Emory VTEU, if back-up isolates are not needed by the central laboratory, they will be tested for heteroresistance in local research lab.

Future-use samples will be batch shipped on dry ice to the DMID Clinical Materials Services (CMS).

## 9. ASSESSMENT OF SAFETY

## 9.1. Specification of Safety Parameters

Safety will be assessed by the frequency and severity of AEs, AESIs, and SAEs.

Levofloxacin, Cefixime, Amoxicillin and clavulanate, and Trimethoprim-sulfamethoxazole are FDA-approved drugs for the treatment of UTI with established and well-described safety profile and NIAID does not expect that any new drug related safety signal will be detected in this trial. As such, the safety data collection will be targeted to collect Suspected Unexpected Serious Adverse Reaction (SUSAR) for all agents, grade 2 and above solicited adverse events and AESIs as specified in this protocol and grade 2 and above unsolicited adverse events and SAEs only for subjects taking 2 or more doses of fosfomycin

# 9.2. Methods and Timing for Assessing, Recording, and Analyzing Safety Parameters

Any deaths, any related SAEs, and AESIs will be sent to the SMC DSMB chair for review within two business days of the DMID's Medical Monitor assessment.

#### 9.2.1. Adverse Events

#### **Adverse Event:**

ICH E6: GCP defines an AE as any untoward medical occurrence in a patient or clinical investigation subject administered a pharmaceutical product regardless of its causal relationship to study drug. FDA defines an AE as any untoward medical occurrence associated with the use of a drug in humans, whether or not considered drug-related.

An AE can therefore be any unfavorable and unintended sign (including an abnormal laboratory finding), symptom, or disease temporally associated with the use of a medicinal (investigational) product. The occurrence of an AE may come to the attention of study personnel during study visits and interviews of a study recipient presenting for medical care, or upon review by a study monitor.

AEs, including solicited adverse events, will be captured on the appropriate data collection form and eCRF. Information to be collected for (un)solicited non-serious AEs includes event description, date of onset, assessment of severity, relationship to study drug, and alternate etiology (assessed only by those with the training and authority to make a diagnosis and listed on Form FDA 1572 as an investigator), date of resolution, seriousness, and outcome. AEs occurring during the trial collection and reporting period will be documented appropriately regardless of relationship. AEs will be followed through resolution.

Any medical condition that is present at the time the subject is screened will be considered as baseline and not reported as an AE. However, if the severity of any pre-existing medical condition increases, it will be recorded as an AE.

All AEs must be graded for severity and relationship to study drug (see definitions). AEs characterized as intermittent require documentation of onset and duration of each episode. The start and stop date of each reported AE will be recorded on the appropriate data collection form and eCRF.

Only Grade 2 and above AEs and SAEs will be reported.

#### **Severity of Event:**

Solicited AEs will be assessed by the investigator using a protocol-defined grading system (Table 4). For unsolicited AEs, the following guidelines will be used to quantify severity:

- Mild (Grade 1): Events require minimal or no treatment; do not interfere with the subject's daily activities.
- Moderate (Grade 2): Events result in a low level of inconvenience or concern with therapeutic measures; may cause some interference with functioning and daily activities.
- Severe (Grade 3): Events interrupt the subject's daily activities and may require systemic drug therapy or other treatment; are usually incapacitating.

Changes in the severity of an AE should be documented to allow an assessment of the duration of the AE at each level of intensity to be performed.

#### **Relationship to Study Drug:**

The assessment of the relationship of an AE to administration of study drug is made only by those with the training and authority to make a diagnosis and listed on Form FDA 1572 as an investigator, and based on all available information at the time of eCRF completion. Whether the AE is related or not is not a factor in determining what is or is not reported in the trial. If there is any doubt whether a clinical observation is an AE, the event should be reported. Only AEs grade 2 and above are reported.

In a clinical trial, study drug must always be suspect. To help assess relatedness, the following guidelines are used:

Related – There is a reasonable possibility that study drug caused the AE, meaning that there is evidence to suggest a causal relationship between study drug and the AE.

Not Related – There is not a reasonable possibility that study drug caused the AE.

#### 9.2.2. Solicited Adverse Events

Solicited AEs are AEs that are common following administration of these types of antibiotics. The solicited AEs will be collected after first dose of study product is given and until the EOT. If subject is on fosfomycin, solicited AEs will be collected for 2 days after last dose of fosfomycin or until EOT, whichever occurs last.

Only grade 2 and above solicited AEs will be reported.

The following Toxicity Grading Scales will be used to grade solicited AEs:

**Table 4: Solicited Adverse Events Grading Scale** 

| Solicited AE      | Mild (Grade 1)  | Moderate (Grade 2)  | Severe (Grade 3)  |
|-------------------|---|---|---|
| Insomnia          | Mild difficulty falling
asleep or staying asleep, or
waking up early  | Moderate difficulty falling
asleep or staying asleep, or
waking up early                  | Severe difficulty falling asleep or staying asleep, or waking up early                        |
| Headache          | No interference with activity   | Repeated use of non-narcotic pain reliever >24 hours, or some interference with activity        | Any use of narcotic pain reliever, or prevents daily activity                                 |
| Dizziness         | No interference with activity, or mild unsteadiness or sensation of movement  | Some interference with activity, or moderate unsteadiness or sensation of movement              | Prevents daily activity, or severe unsteadiness or sensation of movement                      |
| Nausea            | No interference with activity   | Some interference with activity   | Prevents daily activity, or requires IV hydration   |
| Vomiting          | 1-2 episodes in 24 hours  | 3-5 episodes in 24 hours  | >5 episodes in 24 hours, or ER visit, or hospitalization, or requires outpatient IV hydration |
| Constipation      | Occasional or intermittent
symptoms, or occasional
use of stool softeners,
laxatives, dietary
modification or enema | Some interference with activity, or persistent symptoms with regular use of laxatives or enemas | Prevents daily activity, or obstipation with manual evacuation indicated                      |
| Diarrhea          | 3 loose stools or <400
grams/24 hours  | 4-5 loose stools or 400-800 grams/24 hours  | >5 loose stools or >800
grams/24hours, or requires IV
hydration                         |
| Back pain         | No interference with activity   | Repeated use of non-narcotic pain reliever >24 hours, or some interference with activity        | Any use of narcotic pain reliever, or prevents daily activity                                 |
| Rhinitis          | No interference with activity   | Some interference with activity, or local intervention required                                 | Prevents daily activity   |
| Pharyngitis       | No interference with activity   | Some interference with activity, or local intervention indicated                                | Prevents daily activity, or IV therapy indicated  |
| Allergic reaction | Localized rash, or itching without rash   | Diffuse rash covering multiple areas of the body  | Rash requiring clinical visit   |
| Candidiasis       | Mild mucocutaneous candidiasis, requiring no treatment  | Moderate mucocutaneous candidiasis, requiring topical or other over-the-counter treatment       | Severe mucocutaneous candidiasis, requiring urgent  |

|  | clinical evaluation, intravenous |
|--|----------------------------------|
|  | treatment or hospitalization     |

#### 9.2.3. Unsolicited Adverse Events

The unsolicited AEs will be collected only in subjects who receive at least two doses of fosfomycin from the time of second dose of fosfomycin until EOT or 2 days after last dose of fosfomycin whichever occurs last.

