#### 3.2.2. Secondary

- The number of solicited and unsolicited AEs grade 2 and above in subjects receiving fosfomycin for the duration of fosfomycin use until 2 days after last dose.
- The number of serious adverse events (SAEs) in subjects receiving at least two doses of fosfomycin during the trial.
- The difference in rates and severity of solicited AEs in subjects in Strategy 1 and Strategy 2.
- The difference in the proportion of subjects achieving treatment success at EOT between Strategy 1 and Strategy 2.

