## Visit 01: Randomization/Study Drug Initiation (Day 1-3)

The subject/subject's LAR will have completed the informed consent process during the screening period. The subject must be randomized within 48 hours of initiation of screening procedures and must receive study drug the same calendar day as randomization. Screening and randomization can occur on the same day. Treatment assignment will be by randomization.

The following procedures will be completed, according to Appendix A.

- Collection of interim medical history
- Review inclusion/exclusion criteria to verify continued eligibility
- Review of concomitant medications
- Collection of vital signs (blood pressure, heart rate, respiration rate, temperature)
- Limited physical exam (abdominal, flank, and suprapubic palpation, and examination of any other body site as indicated by subject symptomatology)
- Assessment of cUTI signs and symptoms.

- Ensure pregnancy test (serum or urine) for females of childbearing potential is within 48 hours before initiation of study drug
- Enroll subject in AdvantageEDCSM
- Randomize subject
- Discontinue pre-study therapy. Administer first dose of study drug. Investigator-directed adjustment may be needed as detailed in Figure 1.
- The subject will be directly observed at the time of first dosing by a member of the clinical research team. Provide instructions for its subsequent dosing and storage.
- Dispense memory aid and thermometer and provide instructions for their use
- Collection of AEs grade 2 and above and AESI of any grade occurring after the first dose of study drug
- Review urine culture and blood culture results if available

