## 11.4. Final Analysis Plan

Planned analyses of all primary and secondary endpoints will be described in detail in the SAP to be prepared by the DCC and finalized prior to unblinding of the study data.

The primary analysis will be a superiority analysis of treatment success at TOC by study arm in the micro-ITT analysis population. Multiple imputation will be used in the case of missing values for treatment success at TOC in the micro-ITT population. The test of the null hypothesis of no difference between the strategies for the primary outcome (Section 11.1) will be performed using linear regression, and will include site, pyelonephritis, and number of bacterial species detected in the urine at baseline as covariates. Further details of the analysis, including the multiple imputation model, will be described thoroughly in the SAP. As a secondary analysis, a difference in treatment success at EOT by treatment strategy will be tested in the micro-ITT population, using methods analogous to the primary analysis. Sensitivity analyses will be performed for the primary analysis including a complete case analysis in which subjects are analyzed as randomized without imputation and tipping point analyses.

The safety analysis population will include all subjects receiving at least one dose of study drug. 95% confidence intervals of frequencies of solicited and unsolicited adverse events, SAEs and AESIs will be provided using the Wilson score method.

Frequency and number of solicited adverse events of grade 2 and above will be reported by treatment arm, study day, and severity, and differences between treatment arms in frequency of grade 2 and above severity solicited adverse events after the first dose of study drug will be tested using Fisher Exact Tests. For subjects receiving fosfomycin, frequency and number of each solicited adverse event of grade 2 and above severity occurring any time from date of first dose of fosfomycin in subjects receiving 2 or more doses until 2 days after last dose of fosfomycin will be tabulated.

Frequency and number of SAEs in subjects receiving at least two doses of fosfomycin during the trial will be tabulated.

For subjects receiving fosfomycin, frequency of each unsolicited adverse event of grade 2 and above severity occurring in subjects receiving at least two doses of fosfomycin until 2 days after last dose of fosfomycin will be tabulated overall and by MedDRA® System Organ Class and Preferred Term.

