| Randomization                            |                                   | X  |   |                                       |                              |                                     |                        |                   |                            |
| Pregnancy test c              | X                                 |  |   |                                       |                              |                                     |                        |                   |                            |

DMID/NIAID/NIH 86

| Clinical Laboratory  | Serum chemistries d (3 mL) | X  |            |                           |                            |   |   |      |      |      |
|--|---------------------------------------|----|------------|---------------------------|----------------------------|---|---|------|------|------|
|  | Hematology d (4 mL)        | X  |            |                           |                            |   |   |      |      |      |
|  | Urinalysis d                          | X  |            |                           |                            |   |   |      |      |      |
| Future use samples (optional)  |                                       |    |            |                           | Xe 15 ml blood 10 ml urine | (X°)
3 ml
blood
10 ml
urine |   |      |      |      |
| Blood cultures f (32-40 mL)                                     |                                       | X  |            |                           |                            | (Xf)                                    |   | (Xf) | (Xf) | (Xf) |
| Urine specime  | Urine specimen for culture            |    |            |                           |                            | Xg                                      |   | Xg   | Xg   | Xg   |
| Review culture results   |                                       | Xi | Xi         | $\mathbf{X}^{\mathrm{j}}$ |                            |   |   |      |      |      |
| Study drug administration  |                                       |    | X-As Descr | ribed in the S            | Summary-                   |   |   |      |      |      |
| Collection of solicited and unsolicited h grade 2 and above AEs |                                       |    | X          | X                         | X                          | X                                       | X |      | (X)  | (X)  |

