- g. An adequate and appropriate infection specimen should be obtained at the specified time points. If a subject fails treatment at any point in this study, an adequate and appropriate specimen should be obtained. The microorganisms identified from the urine culture will be sent to central study laboratory for susceptibility testing.
- h. Unsolicited grade 2 and above AEs and SAEs will be recorded in subjects receiving at least 2 doses of fosfomycin. A follow up visit on Day 7-14 is done by phone and only for a subject which last dose of oral antibiotic per protocol was fosfomycin.
- i. Review urine culture results if available
- j. Review urine culture results if not available at screening/randomization

DMID/NIAID/NIH 90

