3.2.2. Secondary Endpoints

1. The number of solicited and unsolicited adverse events (AEs) grade 2 and above in subjects receiving fosfomycin for the duration of fosfomycin use until 2 days after last dose.
2. The number of serious adverse events (SAEs) in subjects receiving at least two doses of fosfomycin during the trial.
3. The difference in rates and severity of solicited AEs in subjects in Strategy 1 and Strategy 2.
4. The difference in the proportion of subjects achieving treatment success at EOT between Strategy 1 and Strategy 2.

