9.3.2. Unsolicited Adverse Events

The unsolicited AEs will be collected only in the Fosfomycin Safety Population which includes subjects who receive at least two doses of Fosfomycin from the time of second dose of fosfomycin until EOT or 2 days after last dose of fosfomycin whichever occurs later. The grading scale for AESIs is provided in [Table 4](#).

The number and percentage of subjects reporting at least one unsolicited AE will be summarized by MedDRA SOC and preferred term (PT). A 95% CI will be presented for the percentage of subjects reporting any unsolicited AE (serious or non-serious) for each MedDRA SOC and PT ([Table 46](#)).

The following summaries for unsolicited AEs will be presented by MedDRA SOC, PT, and treatment group:

- Incidence of AEs by severity and relationship to study product ([Table 47](#));
- Incidence of non-serious, related AEs by severity ([Table 48](#));
- Subject listing of non-serious AEs of moderate or greater severity ([Table 51](#));
- Bar chart displaying total frequency of AEs by severity, MedDRA SOC and treatment group ([Figure 5](#));
- Bar chart displaying incidence of AEs by severity, MedDRA SOC and treatment group ([Figure 6](#));

[Listing 11](#) will present details of unsolicited AEs including Subject ID, AE description, AE onset date/end date, relationship to treatment, alternate etiology if not related, outcome, and duration of event (days).

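### Unsolicited AE collection opens at the second fosfomycin dose while secondary endpoint 1 covers all fosfomycin use, so non-serious, non-AESI unsolicited events between doses 1 and 2 fall outside the collection window.

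*Protocol*

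**What the plan says.** Two sections set the collection window. Protocol 9.2.3 restricts unsolicited AEs to subjects with at least two fosfomycin doses and collects them "from the time of second dose of fosfomycin until EOT or 2 days after last dose of fosfomycin whichever occurs last". SAP 9.3.2 repeats this: "from the time of second dose of fosfomycin until EOT or 2 days after last dose of fosfomycin whichever occurs later".

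The first secondary outcome measure in Protocol 3.2.2 takes solicited and unsolicited AEs of grade 2 and above together, "in subjects receiving fosfomycin for the duration of fosfomycin use until 2 days after last dose". SAP 3.2.2, item 1, has the same endpoint.

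Other places bear on the start point:

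- Protocol 11.4 tabulates solicited events in fosfomycin subjects occurring "any time from date of first dose of fosfomycin in subjects receiving 2 or more doses", and SAP 4.5 agrees. For unsolicited events, 11.4 gives the two-dose condition and an end point but no start.
- Protocol 7.2, Visit 01, lists "Collection of AEs grade 2 and above and AESI of any grade occurring after the first dose of study drug".
- Appendix A has a row headed "Collection of solicited and unsolicited" AEs of grade 2 and above, marked from Visit 01. Its note h reads "Unsolicited grade 2 and above AEs and SAEs will be recorded in subjects receiving at least 2 doses of fosfomycin".

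**The concern.** The point is when collection starts in subjects who do take two or more doses, not who belongs to the fosfomycin safety population. One endpoint has two components, and they begin at different times in the same subjects: solicited events at the first dose, unsolicited events at the second. An endpoint defined over all fosfomycin use cannot be fully populated by a collection rule that opens one dose late.

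Assessing the safety of fosfomycin is a secondary objective, and this endpoint is one of its stated measures. Two things are at stake. The unsolicited count tends to be low for the period the endpoint names. And a site that follows the Visit 01 list would record an event that a site following 9.2.3 would not, so ascertainment could vary by site.

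**Working it through.** The plan gives no figure to reproduce. The check sets the passages side by side and then measures the interval.

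**1. Start points**

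| Place | Events | Start |
|---|---|---|
| Protocol 3.2.2, SAP 3.2.2 item 1 | Solicited and unsolicited, grade 2+ | Start of fosfomycin use, so dose 1 |
| Protocol 9.2.3, SAP 9.3.2 | Unsolicited | Dose 2 |
| Protocol 9.2.2 | Solicited | First dose of study product |
| Protocol 11.4, SAP 4.5 | Solicited, two-dose fosfomycin subjects | First fosfomycin dose |
| Protocol 11.4 | Unsolicited, two-dose fosfomycin subjects | Not stated |
| Protocol 7.2, Visit 01 | AEs grade 2+, type not separated | First dose of study drug |
| Protocol 9.1, Appendix A note h | Unsolicited AEs and SAEs | Restricts subjects, not onset |

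The direct conflict is between the first two rows.

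**2. Which events are affected**

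Take a subject who goes on to a second dose, with an event starting after dose 1 and before dose 2.

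- On the 12-term solicited list: collected from the first dose.
- AESI of any grade: collected from Visit 01 (Protocol 7.2, Appendix A).
- Serious: recorded because the subject has two doses; Protocol 9.2.4 sets no second-dose onset limit.
- Anything else of grade 2 or above: inside the endpoint, outside the 9.2.3 window.

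Only the last class is affected.

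**3. Length of the omitted interval**

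Inputs: 5-7 days of oral therapy (Protocol Section 4), assumed here to be all once-daily fosfomycin; endpoint end at last dose plus 2 days (Protocol 3.2.2).

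Window for d once-daily doses = (d − 1) + 2 days. The interval from dose 1 to dose 2 is 1 day.

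| Doses d | Window (days) | From dose 2 (days) | Omitted share |
|---|---|---|---|
| 5 | 4 + 2 = 6 | 5 | 1/6 = 16.7% |
| 6 | 5 + 2 = 7 | 6 | 1/7 = 14.3% |
| 7 | 6 + 2 = 8 | 7 | 1/8 = 12.5% |

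These are shares of time, not of events. The documents give neither an unsolicited AE rate nor a distribution of onset times.

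**The case against.** The strongest case against this point is that little is actually lost. The solicited list covers the common acute reactions, including nausea, vomiting, diarrhea, dizziness, headache and allergic reaction, and runs from dose 1. AESIs and SAEs are not cut off at dose 2, and Protocol 9.1 collects suspected unexpected serious adverse reactions for all agents. A reader might infer that first-dose reactions in continuing subjects are never counted; these provisions show that this goes too far.

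Nor does the gap lie in the tables. A reader might infer that a dose 1 to dose 2 event has no place in SAP Tables 46-48. Those shells use the Fosfomycin Safety Population, which is defined only by two doses; they carry no onset filter, and SAP 9.3 includes every reported AE. An event that was recorded would be tabulated. The fault is in the collection wording.

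Appendix A and Visit 01 are only general support. The Appendix A row combines both event types, so its mark at Visit 01 is needed for solicited events anyway. The Visit 01 line covers both arms, although unsolicited AEs are not collected in subjects who receive only levofloxacin.

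The effect may also be small. Assume a 20% incidence at constant hazard and 31 Strategy 1 subjects (62 ÷ 2). Dropping one day gives 1 − 0.8^(5/6) = 17.0% or 1 − 0.8^(7/8) = 17.7%, a shift of about 0.7 to 0.9 of a subject. And where a subject switches off fosfomycin, 9.2.3 runs on to end of therapy (EOT) if later, which can add events beyond the endpoint's own limit.

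Finally, the second-dose start might be deliberate, or might only mark when a subject qualifies. No section says either, and none says that earlier onsets are then picked up.

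All of this narrows the point. None of it reconciles the endpoint with 9.2.3.

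**Conclusion.** The inconsistency stands in narrow form. In subjects with at least two fosfomycin doses, non-serious, non-AESI unsolicited AEs of grade 2 and above that start between doses 1 and 2 are part of secondary endpoint 1 but fall outside the window in Protocol 9.2.3 and SAP 9.3.2. The unsolicited count tends to be low, and because Visit 01 can be read as asking for these events, capture may differ between sites.

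The omitted day is about 12.5-17% of the window, assuming 5-7 once-daily doses, all fosfomycin. That cannot be turned into a number of lost events without an incidence and an onset pattern that the documents do not supply. If the second-dose start was intended, the endpoint wording needs changing instead; the two cannot both stand. No efficacy result is affected.

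**What to change.** In Protocol 9.2.3 and SAP 9.3.2, change the start of unsolicited collection from the second to the first fosfomycin dose, and keep the two-dose condition on subjects. Give the same start point for unsolicited AEs in Protocol 11.4, which now has none. Record dose 1 to dose 2 events at the existing Day 2-4 contact. For a Strategy 2 subject who first takes fosfomycin at or after that contact, the next scheduled opportunity is the EOT visit.

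Rewording cannot recover events that were not recorded, because the SAP was written after enrolment closed. So the SAP should also state that any dose 1 to dose 2 events on file are included in Tables 46-48, and that collection in that interval may be incomplete.

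The cost is a wording change in three sections, a short SAP statement and, in any trial still enrolling under this text, a little more recall at a contact that already takes place. Reported AE counts may rise slightly.
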